8.5.1.2. Criteria for Calculation and Reporting of Area Under the Concentration-time Curve

The minimum requirement for the calculation of AUC will be the inclusion of at least 3 consecutive concentrations above the lower limit of quantification. If there are only 3 consecutive concentrations, at least 1 should follow C_{max} .

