3. STUDY ENDPOINTS

3.1. Primary Endpoints

The following PK parameters will be calculated whenever possible, based on the plasma concentrations of digoxin and LOXO-305 (as appropriate):

- area under the concentration-time curve from hour 0 to the last measurable concentration (AUC_{0-t})
- area under the concentration-time curve over a dosing interval (AUC_{tau})
- apparent systemic clearance (CL/F)
- maximum observed plasma concentration (C_{max})
- time to maximum observed plasma concentration (t_{max})
- mean residence time based on AUC_{0-t} (MRT_{last})

The following PK parameters will be calculated whenever possible, based on the urine concentrations of digoxin:

- amount excreted in urine per sampling interval (Ae)
- percentage of dose excreted in urine per sampling interval (t_1-t_2) , where $\%f_{eu} = 100$ $(A_{eu}/dose)$
- renal clearance (CL_r)

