7.3. Pharmacokinetic Population

The PK population will consist of all subjects who received a dose of LOXO-305 or digoxin, have at least 1 quantifiable plasma concentration, and for whom at least 1 PK parameter can

be computed. A subject may be excluded from the PK summary statistics and statistical analysis if the subject has an AE of vomiting that occurs at or before 2 times the median t_{max} . The impact of protocol deviations on the PK population will be evaluated on a case-by-case basis.

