8.5.2. Presentation of Pharmacokinetic Data

All PK concentrations and parameters will be listed.

Summary tables, arithmetic mean (+ standard deviation [SD]) figures, overlaying individual figures, and individual figures by treatment and time postdose will be provided for plasma PK concentrations. All PK concentration figures will be produced on both linear-linear and linear-logarithmic scales, with the exception of figures across all days, which will be produced on the linear-linear scale only. The +SD bars will only be displayed on the linear-linear scale.

Summary tables by treatment will be provided for all PK parameters, with the exception of diagnostic regression-related PK parameters. Summary statistics (n, Mean, SD, CV, minimum, median, maximum, geometric mean [Geom Mean] and geometric CV [Geom CV] will be calculated for plasma and urine LOXO-305 PK parameters. Excluded subjects will be listed in the PK parameter tables, but will be excluded from the statistical analysis and summary statistics and noted as such in the tables.

A subject may be excluded from the PK summary statistics and statistical analysis if the subject has an AE of vomiting that occurs at or before 2 times the median t_{max} .

Individual concentrations deemed to be anomalous will be flagged in the listings and excluded from the summary statistics.

For plasma PK concentration data the following rules will apply:

- Values that are BLQ will be set to 0 for the calculation of summary statistics.
- Arithmetic mean or median values that are BLQ will be presented as 0.
- If any BLQ results (treated as 0) are in a series of summarized data, geometric mean and coefficient of variation (CV) of geometric mean will be reported as not calculated (NC).

Urine concentration data will be listed only.

For PK parameters the following rule will apply:

• For the calculation of summary statistics of PK parameters, all not reported (NR) and NC values in a data series will be set to missing.

• The AUC values will be set to NC if they have been calculated using fewer than 3 concentrations, and/or 3 concentrations if the last is C_{max}.

• Geometric mean and CV will not be calculated for t_{max}.

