8.5.3. Pharmacokinetic Statistical Methodology

A statistical analysis will be conducted to investigate the drug-drug interaction on the PK of the following comparisons:

Plasma PK only

• Multiple doses of digoxin coadministered with a single dose of LOXO-305 versus multiple doses of digoxin alone.

Plasma and urine PK

• Multiple doses of digoxin coadministered with multiple doses of LOXO-305 versus multiple doses of digoxin alone.

The natural log-transformed⁴ PK parameters (AUC_{0-t}, AUC_{tau}, C_{max},Ae_{0-x h} and CL_R) will be analyzed using a mixed effect model.⁵ The model will include actual treatment as a fixed effect, and subject as a random effect.

For each PK parameter separately, the least squares mean (LSM) for each treatment, difference in LSMs between the test and reference treatments, and corresponding 90% confidence interval (CI) will be calculated; these values will then be exponentiated to give the geometric least squares mean, geometric mean ratios, and corresponding 90% CI.

Additionally, the pooled estimate (across all treatments) of the within-subject CV will be calculated, and residual plots will be produced to assess the adequacy of the model(s) fitted.

An example of the SAS code that will be used are as follows:

Mixed Model Analysis

```
proc mixed data = <data in>;
  by parcat1n parcat1 pkday paramn param;
  class trtan usubjid;
  model lpk = trtan / cl residual ddfm = kr2;
  lsmeans trtan / cl pdiff = control('1') alpha = 0.1;
  random intercept / subject = usubjid;
  ods output lsmeans = <data out>;
  ods output diffs = <data out>;
  ods output covparms = <data out>;
```

run;

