10. SIGNIFICANT CHANGES FROM THE PROTOCOL-SPECIFIED ANALYSES

The primary endpoint "area under the concentration-time curve from hour 0 to 24 hours (AUC0-24)" has been removed as this is a repeat of the following primary endpoint "area under the concentration-time curve over a dosing interval (AUC_{tau})" since for this study tau is equal to 24 hours.

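### The SAP's three-concentration minimum lets a digoxin profile that stops short of 24 h supply a modelled AUC0-t, and the SAP does not say what happens to AUCtau for such a profile

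*SAP*

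**What the plan says.** SAP 8.5.1.2 sets the minimum for calculating any AUC: "at least 3 consecutive concentrations above the lower limit of quantification". It adds one condition: "If there are only 3 consecutive concentrations, at least 1 should follow" Cmax. SAP 8.5.2 turns the same floor into a reporting rule: "The AUC values will be set to NC if they have been calculated using fewer than 3 concentrations", or from three when the last of them is Cmax. Neither section names a minimum last sampling time or a limit on extrapolation.

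Two plasma AUCs enter the model. AUC0-t is the "area under the concentration-time curve from hour 0 to the last measurable concentration" (SAP 3.1), so its end point moves with the data. AUCtau is the area over a dosing interval; SAP 10 drops AUC0-24 as a duplicate of it, "since for this study tau is equal to 24 hours".

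SAP 8.5.3 analyses both on the log scale, together with Cmax and the urine parameters: "The model will include actual treatment as a fixed effect, and subject as a random effect", and for each test-reference difference the "corresponding 90% confidence interval (CI) will be calculated". Membership of the PK population is easily met: besides having been dosed, a subject must "have at least 1 quantifiable plasma concentration, and for whom at least 1 PK parameter can" be computed (SAP 7.3).

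**The concern.** The comparisons of interest set digoxin exposure on Day 8 (single LOXO-305 dose) and Day 16 (multiple doses) against Day 7 (digoxin alone), within subject. They are meaningful only if the areas being divided cover comparable stretches of time. A count of concentrations does not secure that. Early sampling after an oral dose is normally dense, so three consecutive quantifiable values, one of them after the peak, can all fall within the first few hours. Digoxin's half-life is 1.5 to 2 days (Protocol 1.6), so most of the 24 h area lies beyond those hours.

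If a subject leaves or loses samples part-way through a PK day, the AUC0-t for that day is a partial area that passes every stated test for reporting and modelling. On the log scale it is a large outlier, and with at most 16 subjects a single one moves the ratio. For AUCtau the difficulty is different: the definition requires 24 h, but the SAP does not say what to do when the profile falls short, so the choice would be made after the data are seen.

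**Working it through.** The documents give no power calculation, effect size or within-subject CV (SAP 5), so there is no planned figure to reproduce. The check asks how far one short profile moves the AUC0-t ratio.

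**Inputs from the documents:** half-life 36-48 h (Protocol 1.6); dosing interval 24 h (SAP 10); up to 16 subjects (SAP 5).

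**Assumptions:** one-compartment oral kinetics; absorption rate constant ka 0.7-3 per h; within-subject CV 20%; true ratio 1.25 for illustration; complete profiles compared over 24 h; each contrast treated as a paired comparison of log values.

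**Step 1: share of the 24 h area accrued by time T.** With k = ln 2 / half-life, at steady state f(T) = A(T)/A(24), where

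A(x) = (1 − e^(−kx)) / [k(1 − e^(−24k))] − (1 − e^(−ka·x)) / [ka(1 − e^(−24ka))].

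For half-life 36 h and ka = 1 per h: k = 0.01925, A(6) = 15.31 − 1.00 = 14.31, A(24) = 51.94 − 1.00 = 50.94, so f(6) = 0.28. Superposing the protocol's actual regimen (two doses on Day 1, then daily) gives the same shares on Days 7, 8 and 16 to within 0.001. Over the assumed ranges:

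| Profile ends at | Share of 24 h AUC |
|---|---|
| 4 h | 18-20% |
| 6 h | 27-29% |
| 8 h | 36-38% |
| 12 h | 53-56% |

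**Step 2: shift in the ratio.** One short profile among n complete pairs shifts the mean log difference by ln(f)/n. The ratio is multiplied by f^(1/n) if the cut is on a test day and by f^(−1/n) if it is on Day 7. With n = 16:

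- Cut at 6 h, f = 0.28: ln f = −1.273; −1.273/16 = −0.0796; factor 0.92 on a test day, 1.08 on Day 7. A true 1.25 reads 1.15 or 1.35.
- Cut at 12 h, f = 0.55: ln f = −0.598; factor 0.96 on a test day, 1.04 on Day 7. A true 1.25 reads 1.20 or 1.30.

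A Day 7 cut affects both contrasts, because Day 7 is the reference for each.

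**Step 3: width of the 90% CI.** At CV 20% the variance of a log difference is 2·ln(1 + 0.2²) = 0.0784. One pair shifted by ln f adds (ln f)²/16, which for f = 0.28 is 1.620/16 = 0.1013. The half-width on the log scale is 1.753·√(variance/16), with 15 df.

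| Case | Half-width | Ratio and 90% CI |
|---|---|---|
| All complete | 1.753·√(0.0784/16) = 0.123 (×/÷ 1.13) | 1.25 (1.11-1.41) |
| One test-day cut at 6 h | 1.753·√(0.1797/16) = 0.186 (×/÷ 1.20) | 1.15 (0.96-1.39) |
| One Day 7 cut at 6 h | 0.186 (×/÷ 1.20) | 1.35 (1.12-1.63) |

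A test-day cut pulls the lower limit below 1 but hardly moves the upper limit, because the lower estimate and the wider interval nearly cancel there.

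**Step 4: AUCtau if it were extrapolated.** With the same kinetics, assumed sampling times, no assay noise and a slope through the last three points, the extrapolated AUCtau is 0.999 to 1.085 of the truth for cuts at 6, 8 and 12 h. One such profile in 16 changes the ratio by at most 1.085^(1/16) = 1.005. A distribution phase or noise would alter this. The share being extrapolated is large: with a last sample at 12 h it is 44-47% of AUCtau.

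**The case against.** Four arguments weigh against the point.

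*AUCtau is already protected by its definition.* This stands. A reader might infer that a partial area goes straight into the 24 h exposure ratio. The SAP does not direct that: an area that stops at 6 h is not an AUC over a 24 h interval, and parameters are determined only where possible (SAP 8.5.1). Step 4 also gives no reason to expect a large error from extrapolation in a simple model. For AUCtau the fault is silence, not a wrong instruction. AUC0-t has no such protection.

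*The event is unlikely and its direction is not fixed.* Largely stands. Subjects are confined to Day 20. Safety digoxin samples are predose troughs on Days 7 to 15, and results need only be ready before the following day's dose (Protocol 7.2.6, Appendix 4). A withdrawal prompted by a trough would therefore often fall between profiles, although a Day 8 result could arrive during the Day 8 profile. Acute symptoms or withdrawal of consent could still end sampling mid-day. A reader might infer that the rule systematically hides an interaction. The documents do not support that: they give no frequency for such events, a Day 7 cut exaggerates the ratio, and the upper limit barely changes.

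*Other rules would catch it.* Only in part. Early-termination data are excluded in general, with exceptions allowed, on the ground that they have no scheduled timepoint (SAP 8.1.2); serial PK samples do have one. Deviations are reviewed case by case (SAP 7.3). Replacement for insufficient PK data is optional and undefined (Protocol 4.5). Residual plots would show the outlier but prescribe no action. The outlier rule (SAP 8.5.1.5) concerns implausible concentrations, and those in a short profile are all plausible. SAP 8.5.1.3 does require matching end times for renal clearance, but no such rule covers the modelled plasma AUCs.

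*A 24 h coverage rule does not by itself give AUC0-t a common window.* Correct. SAP 8.5.1 mentions collections to 96 h after the Day 16 dose. The plasma schedule is redacted, so whether this applies to digoxin AUC0-t cannot be settled here; it is a separate question.

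**Conclusion.** The point holds for AUC0-t, and for AUCtau as an unstated rule. The reporting floor counts concentrations and says nothing about coverage, so an incomplete digoxin profile gives a wrong AUC0-t that enters the primary model unless someone intervenes by discretion. Under the kinetics and sample size set out above, one 6 h profile changes the ratio by about 8% in either direction and widens the 90% CI from ×/÷ 1.13 to ×/÷ 1.20. If all profiles are complete nothing changes, and confinement makes a short profile uncommon. It is worth settling because the rule concerns a primary endpoint in an open-label study and is easily fixed before database lock.

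**What to change.** In SAP 8.5.1.2 and 8.5.2, replace the three-concentration minimum with a coverage rule for digoxin AUCs that enter the model:

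- Report AUCtau and AUC0-t for a day only if the sample at or near 24 h postdose is available, with the permitted window stated. Otherwise set that day's AUCs to NC.
- Keep that day's Cmax if sampling covered the peak.
- Keep the subject's other days in the mixed model.

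Do not add an extrapolation fallback. With a last sample at 12 h about 45% of AUCtau would be extrapolated, and the span of two half-lives preferred in SAP 8.5.1.1 means 72-96 h for digoxin, which no 24 h profile can supply.

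The cost is wording, plus the AUC of an occasional incomplete profile, so n falls by one for that contrast. In the example above, 15 pairs (14 df, t = 1.761) give a half-width of 1.761·√(0.0784/15) = 0.127, so 1.25 (1.10-1.42) against 1.25 (1.11-1.41) with all 16. That loss is far smaller than the distortion it prevents.

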8.5.1.3. Calculation of Urinary Parameters

The amount of the dose administered recovered (Ae) in urine for digoxin urine collection interval (t_1-t_2) will be calculated as the product of urine concentration and urine volume.

A total cumulative $Ae_{0-x h}$ will be calculated by summing the Ae_{t1-t2} values over the 0-x h interval, where x = end of the last collection time interval.

The percentage of the administered dose for digoxin recovered over the time interval t1 to t2 (Fe $_{t1-t2}$) will be calculated for each urine collection interval as follows:

Cumulative $fe_{0-x h}$ will be calculated by summing the fe_{t1-t2} values over the 0-x h period in the same manner as $Ae_{0-x h}$.

Renal clearance (CL_R) will be calculated over 0-t according to the following formula, where cumulative Ae and AUC are calculable to the same end time (t):

8.5.1.4. Criteria for Handling Below the Limit of Quantification or Missing Concentrations for Pharmacokinetic Analysis

Plasma concentrations below the limit of quantification (BLQ) will be assigned a value of 0 before the first measurable concentration and thereafter BLQs will be treated as missing. The following rules apply with special situations defined below:

- If an entire concentration-time profile is BLQ, it will be excluded from PK analysis.
- Where 2 or more consecutive concentrations are BLQ at the end of a profile, the profile will be deemed to have terminated and any further quantifiable concentrations will be set to missing for the calculation of the PK parameters, unless they are considered to be a true characteristic of the profile of the drug.
- If a predose plasma concentration is missing, it may be set to the concentration value at 24 hours postdose after repeated QD doses.

Urine concentrations that are BLQ will be set to 0 for the calculation of Ae_{t1-t2} .

8.5.1.5. Treatment of Outliers in Pharmacokinetic Analysis

If a value is considered to be anomalous due to being inconsistent with the expected PK profile, it may be appropriate to exclude the value from the PK analysis. However, the exclusion of any data must have strong justification and will be documented in the CSR.

Any quantifiable predose concentration value will be considered anomalous and set to missing for the PK analysis.

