3.3.2. Digoxin

The selected dose of digoxin is based on typical doses for this drug when used as an index substrate in DDI studies and is considered to be high enough to provide sufficient plasma concentrations to achieve the objectives of the study. Following the initial loading dose and given a $t_{1/2}$ of approximately 1.5 days, digoxin plasma concentrations would be expected to achieve steady-state by Day 7 in the absence of LOXO-305. Day 7 has therefore been selected for the steady-state digoxin PK sampling and Day 8 has been chosen for the first LOXO-305 coadministration. Subjects may be withdrawn if their trough serum digoxin level exceeds 2.0 ng/mL and/or they exhibit clinically significant signs or symptoms of digoxin toxicity.

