8.3.1. Descriptive Analysis

Plasma and urine concentrations and PK parameters will be summarized with descriptive statistics (number, arithmetic mean, standard deviation, coefficient of variation [CV%], geometric mean, geometric CV%, median, minimum, and maximum).

Individual and mean plasma and urine concentration-time curves (both linear and log linear) will be included in the final report.

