8.5. Pharmacokinetic Assessments

8.5.1. Pharmacokinetic Analysis

The following plasma PK parameters will be determined where possible from the plasma concentrations of LOXO-305 and digoxin using noncompartmental methods in validated software program Phoenix WinNonlin (Certara, Version 8.1 or higher):

Parameter	Unitsa	Definition
$\mathrm{AUC}_{0\text{-t}}$	h*ng/mL	area under the concentration-time curve from hour 0 to the last measurable concentration $(t_{last})^b$
$\mathrm{AUC}_{\mathrm{tau}}$	h*ng/mL	area under the concentration-time curve over a dosing interval ^b (tau=24 hours)
C_{max}	ng/mL	maximum observed plasma concentration
t_{max}	Н	time to maximum observed plasma concentration
CL/F	L/h	apparent systemic clearance
$MRT_{last} \\$	Н	mean residence time (based on AUC _{0-t})
AR_{AUC}	NA	accumulation ratio base on AUCtau (LOXO-305 only)

NA Not applicable

For each subject, the following urine PK parameters will be calculated, whenever possible, based on the urine concentrations of digoxin:

Parameter	Unitsa	Definition	
Ae	mg	amount excreted in urine per sampling interval (t1-t2)	
CL_R	L/h	renal clearance	

^a Units are based on concentration units (provided by the bioanalytical lab or preferred units for presentation of PK parameters) and dose units used in the study.

^b Area under the concentration-time curve will be calculated using the linear trapezoidal rule for increasing and decreasing concentrations

%feu	%	percentage of dose excreted in urine per sampling interval (t1-t2),
		where CCI

^a Units are based on concentration units (provided by the bioanalytical lab or preferred units for presentation of PK parameters) and dose units used in the study.

Additional PK parameters may be determined where appropriate, e.g. terminal elimination half-life $(t_{1/2})$ after last dose (Day 16) with sample collections up to 96 hours postdose.

The PK analysis will be carried out where possible using actual blood sampling times postdose. If an actual time is missing, the sample concentration result will be treated as missing unless there is scientific justification to include the result using the nominal time.

The parameters C_{max} and t_{max} will be obtained directly from the concentration-time profiles. If C_{max} occurs at more than 1 timepoint, t_{max} will be assigned to the first occurrence of C_{max} .

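### The SAP sets every quantifiable predose concentration to missing, which in this multiple-dose study deletes genuine troughs and the true hour-0 values of AUC

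*SAP*

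**What the plan says.** SAP 8.5.1.5 ends with the rule "Any quantifiable predose concentration value will be considered anomalous and set to missing for the PK analysis". It makes no distinction by analyte, day or dose number, and it is mandatory. The preceding paragraph sets a different standard for dropping values: "However, the exclusion of any data must have strong justification and will be documented in the CSR".

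Three other SAP provisions bear on the same samples:

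- Section 8.5.1.4, on BLQ values: "Plasma concentrations below the limit of quantification (BLQ) will be assigned a value of 0 before the first measurable concentration".
- Section 8.5.1.4, on missing predose values: "If a predose plasma concentration is missing, it may be set to the concentration value at 24 hours postdose after repeated QD doses".
- Section 8.5.2, on summaries: "Individual concentrations deemed to be anomalous will be flagged in the listings and excluded from the summary statistics".

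Protocol 8.3.1 plans that "Plasma and urine concentrations and PK parameters will be summarized with descriptive statistics". Protocol 3.3.2 expects digoxin to be at steady state by the reference profile: "Day 7 has therefore been selected for the steady-state digoxin PK sampling and Day 8 has been chosen for the first LOXO-305 coadministration". The parameter table in SAP 8.5.1 includes the "accumulation ratio base on AUCtau (LOXO-305 only").

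**The concern.** A quantifiable concentration before a first dose is suspect. One before a seventh or sixteenth day of daily dosing is expected. In the profiles used for the comparisons (Days 7, 8 and 16), the rule makes sense only for LOXO-305 on Day 8. Everywhere else it labels a valid measurement anomalous and deletes it automatically.

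Two things are at stake. First, the measured troughs leave the concentration summaries, although they stay in the listings. The serum digoxin safety troughs cannot stand in for them, because Protocol 7.2.6 keeps those out of the PK evaluation. Second, AUC0-t and AUCtau lose their measured hour-0 value, and the SAP does not say what takes its place. The curve could start at the first postdose sample, hour 0 could be taken as zero, or the optional 24 h substitution could be used. Quantities that divide by AUC (CL/F and CL_R) inherit the error with the opposite sign. If days were handled differently, the error would no longer cancel in the digoxin ratios.

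**Working it through.** **Are the deleted values real?** The dosing schedule in Protocol 3.1 gives 2 + 15 = 17 digoxin doses and 9 LOXO-305 doses. Protocol 1.6 gives a digoxin half-life of 1.5 to 2 days (36 to 48 h), and Protocol 1.4.2 a LOXO-305 half-life of about 20 h. The fraction left after 24 h is 0.5^(24/t½):

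- digoxin: 0.5^(24/36) = 0.63 and 0.5^(24/48) = 0.71
- LOXO-305: 0.5^(24/20) = 0.44

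A one-compartment oral model with the scheduled doses puts the digoxin predose value at 0.66 to 0.75 of Cmax on Days 7 and 16, and at 0.58 to 0.74 on Day 8 (absorption rate 1 to 2/h, digoxin exposure ratio 1.0 or 1.35, all assumed). For LOXO-305 on Day 16 it is about 0.46 to 0.50 of Cmax (absorption rate 1 to 2.5/h). These are large, expected concentrations.

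**Error in AUCtau, by hand.** SAP 8.5.1 specifies linear trapezoids. With first postdose time t₁, the area lost is

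- hour 0 taken as zero: ½·C₀·t₁
- curve starts at t₁: ½·(C₀ + C₁)·t₁

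Divide by AUCtau = 24·Cavg. At steady state with very fast absorption and k = ln2/t½, C₀/Cavg = 24k·e^(−24k)/(1 − e^(−24k)) and C₁/Cavg = 24k·e^(−k·t₁)/(1 − e^(−24k)). With t₁ = 1 h:

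| | C₀/Cavg | C₁/Cavg | Zero: C₀/(2·24) | Dropped: (C₀+C₁)/(2·24) |
|---|---|---|---|---|
| Digoxin, 36 h | 0.787 | 1.225 | 1.6% | 4.2% |
| Digoxin, 48 h | 0.837 | 1.166 | 1.7% | 4.2% |
| LOXO-305, 20 h | 0.641 | 1.423 | 1.3% | 4.3% |

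With t₁ = 0.5 h the figures are about half of these.

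**Full model.** Assumed sampling was at 0, (0.5), 1, (1.5), 2, 3, 4, 6, 8, 12 and 24 h, with digoxin absorption rates of 0.75, 1.5 and 3/h. From Day 8 the assumed scenarios were no interaction, bioavailability ×1.35, clearance ÷1.35, or ×1.2 and ÷1.2 together. Digoxin AUC0-24 relative to the full profile was:

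- hour 0 dropped: 0.958 to 0.983
- hour 0 zero: 0.982 to 0.993
- refilled from 24 h: 1.000 to 1.0025

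**Digoxin ratios, all days handled alike.** The largest shift in Day 8/Day 7 was from 1.1286 to 1.1317 (0.0031). Day 16/Day 7 moved by at most 0.0012.

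**LOXO-305 accumulation ratio.** The SAP does not define the days; Day 16 over Day 8 is assumed. The Day 8 predose value is BLQ and becomes 0, which is correct. The Day 16 value is quantifiable and is deleted, so only the numerator changes. With absorption rates of 1.5 and 2.5/h:

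| Day 16 hour 0 | Ratio | Change |
|---|---|---|
| Kept as measured | 1.79 to 1.81 | none |
| Dropped | 1.72 to 1.77 | −1.8% to −4.2% |
| Zero | 1.77 to 1.79 | −0.7% to −1.4% |
| Refilled from 24 h | 1.79 to 1.81 | 0.0% |

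**Refill for digoxin on Day 8.** The true predose value precedes the first LOXO-305 dose; the 24 h value follows it. With an assumed 1.35-fold effect, the 24 h value is 12% to 14% above the true trough. The effect on AUC is small (at most 0.25%), but the trough would be wrong.

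**The case against.** The best defence is that the sentence is unqualified boilerplate. It sits under an outliers heading, after a test of inconsistency with the expected profile, and Section 8.5.1.4 shows that the authors expect usable predose values after repeated dosing. The two rules can also run in sequence: set to missing, then fill from 24 h. That leaves AUC almost exactly right. Starting the integral after hour 0 fits poorly with AUCs defined from hour 0 or over a full dosing interval, so the 2% to 4% figures are the least plausible variant. The strong-justification sentence can be read as governing case-by-case exclusions, not a prespecified rule. The primary digoxin ratios barely move and Cmax is unaffected in the model. The accumulation ratio is neither a listed endpoint nor a modelled parameter, and no trough parameter or formal steady-state test is planned.

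Much of this stands as a limit on impact. It does not rescue the rule. The refill is optional, and nothing links it to values deleted under 8.5.1.5. Even when applied, it replaces a valid measurement with an imputed one and does not return the measured trough to the summaries. Nor can an analyst quietly ignore the sentence: SAP Section 1 gives the SAP precedence over the protocol's statistical text and requires substantial deviations to be agreed and reported. One further objection is fair: barring the 24 h refill for digoxin on Day 8 needs a stated fallback, which the fix below supplies.

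**Conclusion.** The concern holds and should be fixed before programming. As written, the rule deletes valid predose concentrations of roughly half to three quarters of Cmax in every profile except LOXO-305 on Day 8. That conclusion rests on the SAP wording and the dosing schedule alone, and confidence in it is high.

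The numerical damage is modest and depends on assumptions about sampling times (redacted), absorption rates and the definition of the accumulation ratio. Digoxin AUCtau is between about 4% low and 0.25% high, depending on which unstated hour-0 treatment is used. CL/F shifts correspondingly, by up to 1/0.958 = 1.044, or about 4% high. The digoxin geometric mean ratios are essentially unaffected provided all days are handled alike, which the SAP does not guarantee. Dropping hour 0 on one day and refilling it on another would put a shift of up to about 4% into a primary ratio. The one-sided effect on the LOXO-305 accumulation ratio runs from none to about 4%.

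**What to change.** Replace the last sentence of SAP 8.5.1.5 with wording to this effect:

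> A quantifiable predose concentration is considered anomalous only before a subject's first dose of that analyte (digoxin Day 1; LOXO-305 Day 8). All other predose concentrations are used as measured, as hour 0 of that interval and, where the same draw serves both, as the 24 h sample of the previous interval.

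In SAP 8.5.1.4, limit the 24 h substitution to predose samples that were not obtained, and exclude digoxin on Day 8 from it. State a fallback for that case. The Day 7 predose value is a candidate: it also precedes LOXO-305, and in the model the Day 8 predose value is only 0.6% to 2.0% above it.

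The cost is a few sentences in the SAP, with no new samples or data and no change to the statistical model.
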